	
 The number and percentage of participants with at least a 4-fold increase in Anti-serotype specific IgG* antibody concentration 28 days after each study intervention administration compared to first study intervention administration baseline, with exact 95% CI as measured by in-house ELISA. The number and percentage of participants with Anti-S. Typhi Vi Ag IgG antibody concentrations equivalent to $\geq 4.3 \mu\text{g/mL}$, before and 28 days after each study intervention administration, with 95% CI as measured by in-house ELISA. Unadjusted between-group ratio of GMC with 95% CI between iNTS-TCV groups and iNTS-GMMA and TCV groups will be computed for each anti-serotype specific IgG*, visit, and administration. 
* Anti-S. Typhi Vi Ag total IgG, Anti-S. Typhimurium O Ag total IgG, Anti-S. Enteritidis O Ag total will be tested.
 
The GMCs, GMRs, and ratio of GMC along with 95% CIs will be obtained by exponentiating (base 10) the means and the lower and upper limits of the 95% CIs of the log-transformed values (base 10).
 
For the between-group assessments, the ANOVA model will be fitted based on the participants having a result at both the baseline and the considered time point. Immunogenicity data from full dose group in Europe will be pooled with those from full dose group in Africa if p-value associated to parameter for Center*Treatment interaction from ANOVA model ≥ 0.10 (ie, suggesting that impact of treatment on immunogenicity endpoint does not depend on center).
 
In that case, GMC, GMRs, and ratio of GMC will be calculated for entire full dose group (ie, Europe + Africa) adjusted by center. ANOVA model will include both vaccine group and center group as fixed effects, and adjusted GMC, GMRs, and ratio of GMC will be derived by exponential transformation of the corresponding group contrast in the model.
 
A sensitivity analysis will be performed pooling Europe and Africa data and adjusting treatment effect for center variable, regardless of the center*treatment associated p-value.
 
A second sensitivity analysis will be performed pooling Europe and Africa and adjusting treatment effect for race variable.
 
Finally, subgroup analysis will be performed by race.

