15. IMMUNOGENICITY ANALYSIS

The immunogenicity analysis will be based on the Per-protocol Set for analysis of immunogenicity. If, in any study group at any time point, the percentage of vaccinated participants with serological results excluded from the Per-protocol Set for analysis of immunogenicity is 10% or more, a second-line analysis based on the Full Analysis Set will be performed.

Numerical serology results will be derived from the content of IS.ISORRES in the SDTM dataset. For assays with a specific cut-off, the following derivation rules apply:

IS.ISORRES	Derived value
“NEG”, “-”, or “(−)”	cut-off/2
“POS”, “+”, or “(+)”	cut-off
“< value” and value is <= assay cut-off	cut-off/2
“< value” and value is > assay cut-off	value
“> value” and value is < assay cut-off	cut-off/2
“> value” and value is >= assay cut-off	value
“value” and value is < cut-off	cut-off/2
“value” and value is >= cut-off	value
All other cases	missing

Document: \\dccar2dnetvnasc01p-lan1.quintiles.net\cp_ops\PROJECTS\Glaxo SmithKline\GSK216152_WZA10802\SAP
Author: PPD Version Number: 2.0
Version Date: 07DEC2023

Template No: CS_TP_BS016 – Revision 7
Effective Date: 01Nov2021

Reference: CS_WI_BS005

The following derivation rules will apply in the context of LLOQ values:

- If baseline value is below LLOQ
 - 4-fold is defined as 4 times the LLOQ cut-off value
 - GMR is defined as within-participant GMR against LLOQ/2
- If baseline value is above or equal to LLOQ
 - 4-fold is defined as 4 times the baseline value
 - within-participant GMR is defined as within-participant GMR against the baseline value.

The following immunogenicity variables will be assessed:

Assay Type	Sampling Time Points	Component	Method	Unit of Measure	Number of Participants
Humoral Immunity (Antibody determination)	Stage 1: Days 1, 29, 57, 85, 169 and 197	Anti-S. Typhi Vi Ag total IgG	ELISA	EU/mL [#]	50 (Stage 1) 105 (Stage 2)
		Anti-S. Typhimurium O Ag total IgG		EU/mL	
		Anti-S. Enteritidis O Ag total IgG		EU/mL	

[figure not shown]
CCI

Document: \\dccar2dnetvnasc01p-lan1.quintiles.net\cp_ops\PROJECTS\Glaxo SmithKline\GSK216152_WZA10802\SAP
 Author: PPD Version Number: 2.0
 Version Date: 07DEC2023

Template No: CS_TP_BS016 – Revision 7
 Effective Date: 01Nov2021

Reference: CS_WI_BS005

CCI

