The above tabulations may be performed by LLOQ status at baseline (above or equal to cut-off versus below the cut-off) for all 3 components, data permitting.

Only for S. Typhi Vi component the above tabulations may be performed by Anti-S. Typhi Vi Ag IgG antibody concentrations status at baseline as measured by ELISA ($>=$ [CC1] and $<=$ [CC1], $>=$ [CC1] and $<=$ [CC1]), data permitting.

Linear mixed model with repeated measures (MMRM) will be used to perform pairwise comparison between full doses of iNTS-TCV and iNTS-GMMA + TCV at Day 29, Day 57, Day 85, Day 169 and Day 197. The model will use fixed effects for center, treatment, time point, treatment*time point, center*treatment, baseline immunogenicity value as covariate, and a repeated time point effect within a participant under an unstructured covariance matrix. Variance between the groups will not be considered equal unless the assumption leads to convergence issues. Additional covariance structures and suitable transformation (e.g., log) may be explored to attain convergence and meet model assumptions, respectively. This analysis will be performed for full doses of iNTS-TCV and iNTS-GMMA + TCV from both the stages.

```
proc mixed data=indsn;  by parameter;  
  class subjid center trta avisit;  
  model aval=center trta avisit trta*avisit center*trta baseline/ddfm=satterth;  
  repeated avisit/subject=subjid type=un group=trta;  
  lsmeans trta*avisitn/pdiff cl alpha=0.05;  
  run;
```

In this analysis, immunogenicity data from full dose group in Europe will be pooled with those from full dose group in Africa if p-value associated to parameter for center*treatment interaction from MMRM model ≥ 0.10 (i.e., suggesting that impact of treatment on immunogenicity endpoint does not depend on center). In that case, GMC, GMRs, and ratio of GMC will be calculated for entire full dose group (i.e., Europe + Africa) adjusted by center from the above MMRM model without the center*treatment interaction term.

In case center*treatment interaction term is significant (i.e., p-value <0.1) the following analyses will be performed: 1) main analysis including center*treatment interaction term and GMC ratio separately for Europe and Africa will be produced from model with center*treatment interaction term, 2) sensitivity analysis excluding center*treatment interaction and GMC ratio for pooled Europe and Africa will be produced from model without center*treatment interaction term.

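### SAP Section 15 writes the MMRM with no log step and leaves log optional, which contradicts the GMC ratios that model must deliver and the log10 scale fixed in protocol Table 12

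*SAP*

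**What the plan says.** SAP Section 15 starts from the concentration scale: "Numerical serology results will be derived from the content of IS.ISORRES in the SDTM dataset". Its derivation table then assigns the value itself, the cut-off or half the cut-off. The mixed model for full-dose iNTS-TCV against separate iNTS-GMMA and TCV is coded as "model aval=center trta avisit trta*avisit center*trta baseline/ddfm=satterth". Neither the prose nor the code takes a logarithm of the response or the baseline. Log appears once in the model description, as an option: "Additional covariance structures and suitable transformation (e.g., log) may be explored to attain convergence and meet model assumptions, respectively".

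The section asks this model for ratio-scale output. If the interaction term is dropped, "GMC, GMRs, and ratio of GMC will be calculated for entire full dose group (i.e., Europe + Africa) adjusted by center from the above MMRM". If it is kept, "GMC ratio separately for Europe and Africa will be produced from model with center*treatment interaction term". The choice rests on the "p-value associated to parameter for center*treatment interaction from MMRM model ≥ 0.10".

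Protocol Table 12 (Section 9.4.2) says that GMCs, GMRs and GMC ratios are "obtained by exponentiating (base 10) the means and the lower and upper limits of the 95% CIs of the log-transformed values (base 10", and it derives the adjusted ratios by exponentiating the group contrast. SAP Sections 6.1 and 7.2.7 use log10 for calculating GMCs and GMTs. SAP Section 3.3 lists the Entered Set as the only change from the protocol.

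**The concern.** A GMC ratio is a back-transformed difference of mean logs. A model fitted to untransformed concentrations gives differences of arithmetic means in EU/mL, and exponentiating those gives nothing interpretable. The model as written therefore cannot supply the output that the same section demands of it.

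The scale also governs the pooling rule. The interaction p-value decides whether the pooled Europe and Africa ratio is the main result or a sensitivity result, and whether model-based regional ratios are produced. Additive and multiplicative interaction are different hypotheses, so the answer can change with the scale. Under SAP Sections 4.3 and 4.4 the statistical team is unblinded from the Day 85 interim, and the final analyses follow unblinding. A transformation adopted after looking at model fit would thus be chosen by people who know the allocation.

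This is the only center- and baseline-adjusted comparison of the two full-dose regimens. Protocol Section 9.2 says the sample size was chosen to allow an exploratory comparison of them at Day 197 in Stage 2.

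**Working it through.** **Cell sizes.** Protocol Section 9.2 gives at least 133 evaluable participants out of 155 with 12% dropout per group. Multiplying each group in protocol Table 4 by 0.88 and rounding down gives 3+3+1+14+14+7+39+39+13 = 133, which reproduces the figure. The full-dose cells are therefore 14 per arm in Europe and 39 per arm in Africa.

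**What the raw-scale model estimates.** For lognormal titres with GMC G and log10 SD s, the arithmetic mean is G × exp[(ln10)²s²/2]. The ratio of arithmetic means equals the GMC ratio times exp[(ln10)²(s1² − s0²)/2]. The code allows the arms different variances. With a true GMC ratio of 1:
- SDs 0.5 and 0.4: exp(5.302 × 0.09/2) = 1.27
- SDs 0.6 and 0.4: exp(5.302 × 0.20/2) = 1.70
- SDs 0.4 and 0.6: exp(−5.302 × 0.20/2) = 0.59

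So even the ratio of raw LS means is not the GMC ratio unless the SDs match.

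**Why the interaction test depends on scale.** Let both centers share GMC ratio r and SD s, with comparator GMCs G_E and G_A. The raw-scale interaction is k(r − 1)(G_E − G_A), where k = exp[(ln10)²s²/2]. With s = 0.4, k = 1.53. For G_E = 300, G_A = 100 and r = 0.5, the treatment difference is −229 in Europe and −76 in Africa, an interaction of −153. On log10 it is zero.

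At r = 1 the raw interaction is also zero, but the test is still miscalibrated. Raw variance scales with the square of the GMC, while the code separates variances by treatment and not by center. Let v be the smaller within-center variance.
- Europe three times Africa: the pooled variance per arm is (13×9 + 38)v/51 = 3.04v, so the model variance of the contrast is 2 × 3.04v × (1/14 + 1/39) = 0.590v. The true variance is 2 × (9/14 + 1/39)v = 1.337v. The true SE is √(1.337/0.590) = 1.51 times the model SE, which implies rejection near 27%.
- Africa three times Europe: the same steps give a model variance of 1.351v and a true variance of 0.604v, an SE ratio of 0.67 and rejection near 1%.

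**Simulation.** 20,000 trials per scenario; lognormal titres; one visit; 14/14 and 39/39; variance by treatment arm; Satterthwaite df; no baseline covariate or repeated visits. The documents give no SD or center GMC, so these are assumed. The table shows P(interaction p < 0.10) with the same true GMC ratio in both centers and SD 0.4.

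| Europe GMC / Africa GMC | log10, all ratios | raw, ratio 1 | raw, ratio 0.67 | raw, ratio 0.5 |
|---|---|---|---|---|
| 1 | 9.6–10.3% | 9.9% | 10.2% | 9.4% |
| 3 | 9.8–10.3% | 27.8% | 35.0% | 48.2% |
| 5 | 9.8–10.1% | 32.0% | 44.6% | 62.9% |
| 1/3 | 9.8–10.3% | 1.6% | 5.0% | 13.8% |
| 1/5 | 9.7–10.2% | 0.7% | 5.4% | 22.3% |

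Over SDs from 0.3 to 0.6, log10 stays at 9.3–10.5%. Raw spans 0.7–81.2% when center GMCs differ and stays near 10% when they are equal.

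**A real interaction.** With a GMC ratio of 0.5 in Europe and 1.0 in Africa, and Europe's GMC one third of Africa's, detection falls from 52% (log10) to 3% (raw) at SD 0.4, and from 39% to 3% at SD 0.5.

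**The case against.** The strongest reply is that log10 is plainly intended. Protocol Table 12 fixes it, SAP Sections 6.1 and 7.2.7 use it for GMCs, the model is asked for GMC ratios, and AVAL could hold log10 values in the analysis dataset. The table shells, which might settle this, are not among the documents reviewed. This stands so far: the documents contradict themselves, but they do not show that the analysis will be run on raw titres. It does not remove the gap. No text applies log10 to the mixed model, and if AVAL were already logged, offering log as a possible later step would serve no purpose.

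Four stronger readings are tempting, and the documents do not support them.
- A reader might take this as the only model-based comparison. SAP Section 15 also plans an unadjusted between-group model at each visit, which depends neither on the MMRM nor on the pooling test.
- A reader might infer that any difference in titre level between centers creates a raw-scale interaction. At a GMC ratio of 1 with equal SDs it does not. The excess there comes from unequal center variances, and with a separate variance per cell the rejection rate is about 8–9%.
- A reader might infer that the p-value decides whether a pooled analysis exists. SAP Section 15 runs the pooled analysis in every case; the p-value sets its status and whether regional ratios are added.
- A reader might see a confirmatory error rate at risk. Protocol Sections 9.1 and 9.6.2 state no hypothesis, no power and no multiplicity adjustment for these comparisons.

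The simulation is a simplification, and its largest rates need both a three- to five-fold center difference and a two-fold treatment effect.

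**Conclusion.** The point holds as an inconsistency that should be corrected. As written, the MMRM conflicts with its own required output and with protocol Table 12, and the scale of the pooling test is left open until after unblinding. The effect on that test needs center GMCs to differ. Protocol Section 4.2 makes this plausible, because the design sets low against high endemicity, but no center GMC is given. Under the assumed SD of 0.4 and three- to five-fold differences, raw-scale rejection runs from about 1% to 63% against 10% on log10, so the pooling decision can move either way. These rates are illustrative. What is at stake is the validity and labelling of an exploratory ratio; descriptive GMCs, within-participant GMRs and seroresponse rates are unaffected. Confidence is high on the wording gap and lower on how the analysis would be programmed.

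**What to change.** In SAP Section 15, state log10 of the concentration as the response and log10 of baseline as the covariate, for all antigens and visits. Half-cut-off substitution already keeps the values positive. Run the center*treatment test on that model and back-transform contrasts and confidence limits by 10^x to GMC ratios. Delete the optional-transformation wording; a fallback covariance structure for convergence can stay. State log10 for the unadjusted between-group model in the same section too, since it also names the results as dependent variable with no log step. The cost is SAP wording and a few lines of code, with no change to data collection or sample size.

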- Separate administration of low doses of iNTS-GMMA and TCV vaccines in different arms, or
- Placebo and saline in different arms.

The 10 sentinel participants in Step 1 will receive the first study intervention on consecutive days and a telephonic safety follow-up call will be performed on the next day. If the participants have any complaints, they will be invited to the study site for an evaluation of the possible AEs and holding rules, prior to administration of study intervention in the next participant. If the Investigator becomes aware of a holding rule being met, he/she must suspend administration of the study intervention and inform the Sponsor's delegate immediately who will in-turn inform the Sponsor.

The iSRC will review all safety data collected up to 7 days after the first study intervention in Step 1. Step 2 will only commence if there is a favorable safety assessment during this review.

In Step 2, 40 healthy European adults will be randomized in a 2:2:1 ratio. A staggered approach will be followed for the first 10 sentinel participants and these participants will be followed up with a safety follow-up call on the next day of administration of study intervention. If the participants have any complaints, they will be invited to the study site for an evaluation of the AEs and holding rules, prior to administration of study intervention in the next participant. If the Investigator becomes aware of a holding rule being met, he/she must suspend administration of the study intervention and inform the Sponsor's delegate immediately who will in-turn inform the Sponsor. The remainder of the 30 participants will receive the study intervention in a sequential (at least 60 minutes apart) manner. The participants in Step 2 will receive:

- The full dose of the candidate iNTS-TCV vaccine and concomitant saline to be administered in different arms, or
- Separate administration of full doses of iNTS-GMMA and TCV vaccines in different arms, or
- Placebo and saline in different arms.

For the trial to proceed to Stage 2, a favorable evaluation of all available safety data by the iSRC following the first and second study intervention administrations (up to 28 days after second administration) in Step 2 of Stage 1 will be required. In case a No-Go decision is made, the study will be terminated at the end of Stage 1 and there will be no further administration of the study intervention in Step 2.

4.1.2 Stage 2

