In Stage 2 (Africa), a total of 105 healthy African adults, randomized in a 3:3:1 ratio, will receive:

- The full dose of the candidate iNTS-TCV vaccine and concomitant saline to be administered in different arms, or
- Separate administration of full doses of iNTS-GMMA and TCV vaccines in different arms, or
- MenACWY (Menveo) and saline for the first administration, TdAP (Boostrix) and saline for the second administration and Typhim Vi and saline for the third administration in different arms. This is the Control_Stage 2 group.

The first 21 participants in Stage 2 will initially be recruited with administration proceeding sequentially, at least 60 minutes apart. These participants will be followed up with a safety follow-up call on the next day of administration of study intervention. If the participants have any complaints, they will be invited to the study site for an evaluation of the possible AEs and holding rules, prior to administration of study intervention in the next participant. If the Investigator becomes aware of a holding rule being met, he/she must suspend administration of the study intervention and inform the Sponsor's delegate immediately who will in-turn inform the Sponsor. All safety data from these participants up to 7 days after the first administration of the study intervention will be reviewed by the iSRC and the recruitment of the remaining 84 participants in Stage 2 will only commence if there is a positive evaluation by the iSRC. The study interventions will be administered in parallel in the remaining 84 participants.

All 155 participants (Stage 1 and Stage 2) will be closely observed for a minimum of 60 minutes after each study intervention administration, before leaving the facilities. The Investigator will decide if the participant should be observed for more than 60 minutes after each study intervention administered, if required.

Table 4 Study Groups, Intervention, and Blinding

Study groups			Number of participants	Age (Min-Max)	Study interventions first administration	Study interventions second administration	Study interventions third administration	Blinding Visit 1→Visit 10 (Observer-blind)*	
					iNTS-TCV low dose	iNTS-TCV low dose	iNTS-TCV low dose		
Stage 1 (50 participants)	Step 1 (10 participants)	1	Invasive nontyphoidal Salmonella-typhoid conjugate vaccine (iNTS-TCV) low dose	4	18 – 50 years	Saline	Saline	Saline	X

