9.2 Sample Size Determination

A total of 155 participants are planned to be randomized to achieve at least 133 evaluable participants in the Per Protocol analysis set for immunogenicity, assuming a 12% dropout rate for each group. Participants who withdraw from the study will not be replaced.

No confirmatory objectives are planned in this trial; however, the sample size was chosen to allow an exploratory comparison of immunogenicity 28 days after the third administration in Stage 2 (Day 197), between participants receiving full dose of candidate iNTS-TCV vaccine and separate full doses of iNTS-GMMA and TCV vaccines, with respect to Anti-*S. Typhi* Vi Ag total IgG, Anti-*S. Typhimurium* O Ag total IgG, Anti-*S. Enteritidis* O Ag total IgG.

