The following Table summarizes the statistical analyses:

Document: \\dccar2dnetvnasc01p-lan1.quintiles.net\cp_ops\PROJECTS\Glaxo SmithKline\GSK216152_WZA10802\SAP
Author: PPD Version Number: 2.0
Version Date: 07DEC2023

Template No: CS_TP_BS016 – Revision 7
Effective Date: 01Nov2021

Reference: CS_WI_BS005

Starting Model	P-value for Center*Treatment Interaction	Main Analysis Model	Sensitivity Analysis
center, treatment, center*treatment	≥0.1 drop center*treatment from the model	Starting model without center*treatment term	No sensitivity analysis
time point, treatment*time point, baseline immunogenicity value as covariate	<0.1	Same as the starting model. Output GMC ratio from model with interaction, separately from Europe and Africa	Starting model without center*treatment term

In other words, analysis pooling Europe and Africa data adjusting treatment effect for center variable will be performed in all cases, however in case center*treatment interaction parameter is statistically significant at 0.1 level, it will be considered as sensitivity analysis.

A sensitivity analysis may also be performed pooling Europe and Africa and adjusting treatment effect for race variable if there is evidence of different races at the two centers.

CCI

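### A center-by-treatment p-value of 0.10 or more is taken to suggest that the vaccine contrast is the same in both centers and makes the pooled ratio the main result, an inference the test is not shown to be able to support

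*SAP*

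**What the plan says.** SAP section 15 compares the two full-dose regimens (iNTS-TCV v iNTS-GMMA + TCV) across both stages in a repeated-measures model. Its fixed effects are center, treatment, time point, treatment by time point, center by treatment, and the baseline value. The European and African data are pooled "if p-value associated to parameter for center*treatment interaction from MMRM model ≥ 0.10", a result glossed as "suggesting that impact of treatment on immunogenicity endpoint does not depend on center".

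The summary table in the same section turns this into a choice of main analysis:

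- **p of 0.10 or more:** the main model is "Starting model without center*treatment term", and the sensitivity column says that there is none.
- **p below 0.10:** the model with the interaction is main and gives separate ratios for Europe and Africa. The pooled model becomes the sensitivity analysis.

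Protocol section 9.4.2 (Table 12) has the same threshold and the same gloss, with an ANOVA: "Immunogenicity data from full dose group in Europe will be pooled with those from full dose group in Africa if p-value associated to parameter" for the interaction is at least 0.10.

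Two further passages matter. Protocol section 4.2 says the two-stage design is there to assess the vaccine in settings of low and high endemicity and to see whether environmental exposure affects the response. Protocol section 9.2 says the sample size was chosen for the Stage 2 contrast at Day 197.

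**The concern.** The rule treats failure to detect an interaction as a sign that there is none. That is reasonable only if the test would probably have detected a difference large enough to matter, and neither document says what such a difference would be or how likely the test is to find it.

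The practical loss is in what gets reported. When p is 0.10 or more, the model-based European and African ratios are not called for. In neither branch is the ratio of the two ratios given with a confidence interval, yet that is the quantity a reader needs in order to judge whether pooling is sensible. The question the two-stage design was meant to answer is then settled by a p-value, and the designated main result is an average over two populations rather than the African contrast for which the trial was sized.

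**Working it through.** **The plan's own figure.** The nine groups have 4, 4, 2, 16, 16, 8, 45, 45 and 15 participants, with "assuming a 12% dropout rate for each group". Rounding 0.88n down in each group gives 3 + 3 + 1 + 14 + 14 + 7 + 39 + 39 + 13 = 133, the stated evaluable number. The full-dose arms are therefore 14 v 14 in Europe ("In Step 2, 40 healthy European adults will be randomized in a 2:2:1 ratio") and 39 v 39 in Africa ("a total of 105 healthy African adults, randomized in a 3:3:1 ratio, will receive").

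**Assumptions not in the documents.** A common SD of log10 concentration, taken over 0.3 to 0.7, and a two-fold difference between the centers' ratios (log10 2 = 0.301). The common SD is a simplification: under the SAP, "Variance between the groups will not be considered equal unless the assumption leads to convergence issues".

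**Single-visit power, no baseline adjustment.** SE = SD × √(2/14 + 2/39) = 0.4406 × SD. At SD 0.5, SE = 0.2203 and 0.301/0.2203 = 1.366. Normal power at two-sided 0.10 is Φ(1.366 − 1.645) = 39.0%; the noncentral t with 102 df gives 38.8%. Over the range (noncentral t):

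| SD (log10) | Power for two-fold |
|---|---|
| 0.3 | 73% |
| 0.4 | 52% |
| 0.5 | 39% |
| 0.6 | 31% |
| 0.7 | 25% |

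At SD 0.5, power is 21% for a 1.5-fold and 69% for a 3-fold difference. With no dropout (16 and 45 per arm) the two-fold figure is 42.5%. For 80% power on this basis, either the SD must be about 0.27 or, at SD 0.5, the difference must be about 3.5-fold.

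**Closer to the SAP's term.** The model has no center-by-treatment-by-time term, so the tested term is averaged over five post-baseline visits and adjusted for baseline. With equal between-visit correlation ρ and correlation r of each visit with baseline, the variance is multiplied by (1 + 4ρ)/5 − r². At SD 0.5:

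- Averaging only (r = 0): 41%, 47%, 54% and 66% for ρ = 0.9, 0.7, 0.5 and 0.3.
- Baseline adjustment only, one visit: 41% to 60% for r = 0.3 to 0.7.
- Both, with ρ from 0.9 to 0.5 and r from 0 to 0.5: about 41% to 74%. The top value is at ρ = r = 0.5, with factor 0.6 − 0.25 = 0.35.

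Favourable cases go higher: SD 0.3 with ρ = 0.5 and r = 0 gives 90%.

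**Effect of pooling.** With equal variances Europe has weight 14/53 = 0.264. A two-fold difference moves the pooled log ratio from the African one by 0.264 × 0.301 = 0.0795, a factor of 10^0.0795 = 1.20. True ratios of 0.5 (Europe) and 1.0 (Africa) pool to 0.5^0.264 = 0.83; the reverse pools to 0.5^0.736 = 0.60.

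**Does the selection step damage the interval?** At SD 0.5 the pooled SE is 0.5 × √(2/53) = 0.0971, and 0.0795/0.0971 = 0.819. Coverage of the African ratio by the pooled 95% CI is Φ(1.96 − 0.819) − Φ(−1.96 − 0.819) = 87%. In simulation it is 87% over all trials and 87% among those with p of 0.10 or more, while coverage of the pooled ratio itself stays at 95%. The covariance of the pooled estimate with the interaction contrast is SD² × [(14/53)(2/14) − (39/53)(2/39)] = 0, so selecting on the test leaves the pooled estimate's behaviour essentially unchanged.

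**The case against.** The case for leaving the plan alone has real force:

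- There are no hypotheses or confirmatory objectives. Protocol section 9.6.2 says that comparisons are exploratory and that the study is not powered for them.
- Both branches are prespecified, and no decision hangs on which one is called main.
- Unadjusted ratios with 95% CIs are planned by stage, visit and antigen whatever the p-value, including Stage 2 at Day 197. The rough size of any interaction can be read from them.
- The pooled result is labelled as Europe plus Africa. The SAP writes of suggesting, not of showing.

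All of this stands and limits the weight of the point. It does not supply the model-based center ratios or an interval for the interaction when p is 0.10 or more, and it does not make the inference sound.

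Three stronger readings are tempting, and the documents support none of them:

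- **That the test has 39% power.** That figure needs an SD of 0.5 log10, a two-fold target and a single unadjusted visit. None of these is in the documents, and the SAP's own term would do better.
- **That the pooled interval is invalid because the model was selected on the same data.** The 87% coverage arises from comparing an average of two populations with one of them. Always pooling would give the same figure.
- **That the three antigens will often end up with different main models by chance.** With no interaction, the chance that at least one is split is 1 − 0.9³ = 27% if the antigens are independent. They are measured in the same people, and positive correlation would lower it, so 27% is an upper-end value. A split also removes nothing, since the pooled ratio is still reported.

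**Conclusion.** The concern holds in limited form. A center-by-treatment p-value of 0.10 or more is weak grounds for suggesting that the contrast does not depend on center, and it should not decide which result is main. For a single unadjusted visit, power for a two-fold difference is 73% to 25% over SD 0.3 to 0.7. For the SAP's term it is higher, about 41% to 74% at SD 0.5 under moderate to high assumed correlations, and above 80% in favourable cases. The conclusion does not need a particular value: no power is claimed anywhere, and adequate power cannot be established from the documents.

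The consequence is moderate: with a true two-fold difference, a pooled main ratio sits a factor of about 1.20 from the African one, given equal variances and 12% dropout in each arm. This is a cheap improvement of minor to moderate weight.

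**What to change.** In SAP section 15, for every antigen and whatever the p-value:

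1. Output the model-based Europe and Africa ratios, and the ratio of the two ratios with its 95% CI. Without a three-way term, the last is one number per antigen. The printed code asks only for treatment-by-visit means, so it needs added estimate statements.
2. Keep the center-adjusted pooled ratio, which the SAP already produces in all cases.
3. Fix the roles in advance: center-specific ratios main, pooled ratio supportive.
4. Report the interaction p-value descriptively and remove its use as a switch.
5. Delete the gloss on independence from center.

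Make the matching changes in protocol Table 12, or record the departure in SAP section 3.3.

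The cost is wording, a few lines of code and a few more table rows, with no new data. The one real downside is that the pooled estimate loses its main label when p is 0.10 or more.
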